## 2.4 – Statistical Analysis

The demographic and clinical characteristics of male patients age 18 or older with prostate cancer who are eligible and electing to undergo robotic assisted laparoscopic prostatectomy (RALP) at OhioHealth Dublin Methodist Hospital (DMH) Robotic Urology with the Principal Investigator will be reported using means and standard deviations or medians and interquartile ranges for continuous variables, or frequencies and percentages for categorical variables. We plan to compare the clinical outcomes of patients between different insufflation pressures (6 versus 15 mmHg). Continuous variables will be compared between two groups using independent sample t-test or Mann-Whitney U test, as appropriate, and categorical variables will be compared using Chi-square test or Fisher's exact test, as appropriate.

During the previous feasibility study of RALPs at an insufflation pressure of 6 mmHg, we found that there was a significant difference in pain scores at 5-12 hours. The average score in the 6 mmHg group was 3.2, and that in 15 mmHg historical group was 3.9. Using these values and an assumed standard deviation within each group of 1.4 (effect size = 0.5), at a significance level of 0.05 to achieve 90% power, the estimated sample size will be 86 patients in each group (total 172 patients). However, to account for ineligible patients after enrollment (estimated 10%), we will enroll minimum of 192 patients.

**Aim #1) Compare average postoperative pain medication use between groups, as measured in total morphine equivalents (MME) over time at pre-specified time intervals through follow-up at 1 week.**

Postoperative medication use between the two groups will be assessed at the following time points: during the PACU stay, during the first 4 hours on the floor, next 8 hours, the following 8 hours, and following discharge through the 1-week follow-up visit. Both total and average medication use measured in total morphine equivalents at/during each time point will be calculated and compared between two groups (6 versus 15 mmHg) using independent sample t-test or Mann-Whitney U test, as appropriate.

**Aim #2) Compare average and maximum postoperative pain scores between groups, as measured using the self-reported 11-point numerical rating scale (NRS), over time at pre-specified time intervals through discharge.**

Similar to aim 1, postoperative pain scores will be assessed at following time points: during the PACU stay, during the first 4 hours on the floor, next 8 hours, and the following 8 hours, as well as the final scores immediately prior to discharge (or via phone call if discharged same-day). There will be only one measurement of pain at each bodily location during the PACU stay, as well as at discharge. However, the average and maximum postoperative pain scores will be calculated for each of the time intervals (the first 4 hours on the floor, next 8 hours, and the following 8 hours). The comparison of average and maximum scores at each time point between the two groups will be performed using independent sample t-test or Mann-Whitney U test, as appropriate.

The association between patient demographic or clinical characteristics and differences in medication use or pain scores will be assessed using multivariate regression. The appropriate type of regression (logistic or linear) used will be determined after data collection is complete.

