Since first described in 2001, robotic assisted laparoscopic prostatectomy (RALP) has been traditionally performed at a pneumoperitoneal insufflation pressure of 12-15 mmHg, derived from standard practice used during laparoscopic surgeries. Abdominal insufflation with carbon dioxide causes a multitude of known physiologic changes including increased peak airway pressures, depressed cardiac output, oliguria, and systemic acidosis, many of which show dose-dependent improvement with the reduction of intraoperative pressures.

Reducing intraperitoneal stretch with lower intra-abdominal pressures may also improve postoperative pain and facilitate earlier hospital discharge as evidenced by studies in general surgery comparing outcomes following laparoscopic cholecystectomy. Despite these results, few surgeons perform RALP at reduced pressure likely due to habit or the perceived concern for poorer visibility, compromised hemostasis, and/or technical difficulty. Furthermore, some have even proposed performing RALP at an increased pressure of 20 mmHg in an effort to achieve better hemostasis despite other physiologic consequences. There remains a paucity of data exploring the feasibility and potential benefits of performing RALP at low insufflation pressures, and no studies have explored how high the pneumoperitoneal pressure must be to perform RALP or, in other words, the minimum pressure that is adequate.

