**Table 1. Study Variables.**

Category	Data points
Enrollment Log	

1. MRN

2. Name

3. DOB

4. Date of consent

5. DOS/randomization

6. Enrolled (y/n)

7. Randomized (y/n)

	

8. Randomization envelope (#)

9. Withdrawn (y/n)

10. Reason withdrawn (if applicable)

Demographics	

1. Phone number

2. BMI (kg/m^2)

3. Weight (lbs)

4. Medical history (free text)

5. Surgical history (major only; free text)

6. Serum creatinine (most recent prior to surgery) (mg/dl; date)

7. Hemoglobin (most recent prior to surgery) (g/dl; date)

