Intraoperative	

1. Details of the surgical procedure (free text)

2. Port number/size(s)/locations (standard protocol -or- deviation from standard protocol) – if deviation, explain

3. Continuously recorded values (only means/standard deviations recorded in REDCap) – as measured by Anesthesia

a. End tidal CO2 (mmHg)

b. O2 saturation (%)

c. Respiratory rate (bpm)

d. Blood pressure (mmHg)

e. Heart rate (bpm)

f. Tidal volume (ml)

g. PIP (peak inspiratory pressure) (mmHg)

h. PEEP (positive end-expiratory pressure) (mmHg)

4. Core body temperatures (F) – as measured by Anesthesia

a. After trocar placement (baseline)

b. 30 minutes

c. 60 minutes

d. End of procedure

5. Insufflation time (minutes)

6. Insufflation pressure (6 or 15 mmHg)

7. Increased pressure episodes necessary to successfully complete the procedure (# times)

a. Time of each adjustment (hh:mm)

b. Level of each adjustment (mmHg)

8. Significant loss of pneumoperitoneum (# times)

a. Time of each adjustment (hh:mm)

b. Level of each adjustment (mmHg)

9. Pressure range (lowest and highest; mmHg)

10. Smoke evacuation quality (below average, average, above average)

11. Total amount of gas used during the procedure (l)

12. Scope cleanings (#)

13. Malfunctions of the AirSeal iFS or control devices (# times)

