	

14. Estimated blood loss (EBL; ml)

15. Obturator artery manipulation (no, left, right, bilateral) – only on Case Sheet (Appendix F)

16. Console time (minutes from initial incision to closure)

17. Use of intraoperative pain medication

a. Fentanyl (y/n)

i. Dose (mg)

ii. Morphine equivalents (MME)

b. Toradol (y/n)

i. Dose (mg)

18. Pathology report

a. Pathological Stage

b. Clinical Stage (T1a-c, T2a-c, T3a-c)

c. Gleason Score (ranging from 6-10: 3+3=6, 3+4=7, 4+3=7, 3+5=8, 5+3=8, 4+4=8, 4+5=9, 5+4=9, 5+5=10)

d. Margins (positive/negative)

e. Extra prostatic extension (EPE; y/n)

f. Tumor quantification (%)

Postoperative (PACU & Floor)	

1. Recorded in PACU

a. Vital signs recorded in PACU setting

i. Time

ii. Respiratory rate (bpm)

iii. Blood pressure (mmHg)

iv. Heart rate (bpm)

v. Temperature (F)

b. Other PACU assessments

i. O2 saturation (%) (first recorded)

ii. Post-operative nausea and vomiting (y/n for each)

iii. Wound infection (y/n)

c. Time in PACU (hours)

i. Arrival & discharge times (hh:mm)

2. Recorded on Floor

a. Vital signs first recorded in non-PACU setting (i.e., on the floor)

i. Respiratory rate (bpm)

ii. Blood pressure (mmHg)

iii. Heart rate (bpm)

iv. Temperature (F)

b. Other non-PACU / Floor assessments

i. Labs drawn (y/n)

1. Serum creatinine (mg/dl; date)

2. Hemoglobin (g/dl; date)

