according to routine care using the AirSeal iFS, and all clinical decisions will be made per standard practice and policy. [name] (the PI) will be the only surgeon performing these procedures, eliminating any variation in technique between surgeons. Participants in this study are not exposed to any additional or different risks associated with the surgery, as all patients will undergo insufflation. Following trocar placement, initial insufflation will be performed at 6 mmHg for patients in the study group and 15 mmHg for patients in the control group. If required, insufflation pressures for the study group will be increased up to 15mmHg per standard surgeon protocol. Increased insufflation pressure will be maintained either transiently (≤5 minutes to control bleeding or to improve access/visualization) or for the duration of the procedure as per surgeon need. The amount of time at each insufflation pressure will be recorded.

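### Hemoglobin, creatinine and core temperature have collected baseline values, but the plan neither defines the quantity compared nor adjusts for baseline, which costs precision on supporting variables

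*Combined protocol and SAP*

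**What the plan says.** Table 1 (section 2.2) lists two preoperative laboratory values among the demographics: "Serum creatinine (most recent prior to surgery) (mg/dl; date") and "Hemoglobin (most recent prior to surgery) (g/dl; date"). Both appear again among the floor assessments, for example "Hemoglobin (g/dl; date"), nested under a yes/no item for whether labs were taken. The intraoperative block lists four core temperatures. The first is "After trocar placement (baseline"); the others are at 30 minutes, 60 minutes and the end of the procedure.

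Section 2.4 has one general rule for such variables: "Continuous variables will be compared between two groups using independent sample t-test or Mann-Whitney U test, as appropriate". Its only covariate model is confined to Aims 1 and 2: patient characteristics and "differences in medication use or pain scores will be assessed using multivariate regression". Section 2.4 mentions neither change from baseline nor adjustment for an outcome's own baseline.

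None of the three variables appears in Aims 1 to 4, which concern opioid use, pain scores, tidal volume and length of stay.

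**The concern.** Two things are left open. First, the analysed quantity is undefined. The general rule fits a test on the postoperative hemoglobin equally well as a test on the fall from the preoperative level. These tests differ in precision, and the choice could be made after the data are seen. Second, under either reading the most efficient standard use of the baseline is not planned, although the baseline is already in the database.

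The stake is modest but real for hemoglobin. Section 1.1 explains the limited use of reduced pressure partly by the "perceived concern for poorer visibility, compromised hemostasis, and/or technical difficulty". Section 2.3 states that only treatment-related serious adverse events are tracked, so information on non-serious bleeding comes mainly from estimated blood loss and hemoglobin. Blood loss is an estimate from a case in which the single operating surgeon controls the pressure; hemoglobin is a laboratory value. A postoperative hemoglobin carries each patient's preoperative level as well as the loss, and that part of its variance can be removed at no cost.

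**Working it through.** **The plan's own figure.** Section 2.4 uses pain scores at 5–12 hours: means 3.2 and 3.9, SD 1.4, alpha 0.05, power 90%.

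- Normal approximation: n = 2 × (1.960 + 1.282)² × (1.4/0.7)² ≈ 84.1, so 85 per arm.
- The t-based solution is 85.03, so 86 per arm, as stated. Two-sided alpha is needed: one-sided gives 69.
- 172/0.90 = 191.1, so 192, as stated.

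The stated sample size reproduces and is not affected by this point. It concerns pain only. The documents give no SD, expected difference or correlation for hemoglobin, creatinine or temperature.

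**Inputs for the check.** 86 per arm comes from section 2.4. The correlation rho between baseline and later value is assumed and shown as a range. Differences are expressed in SDs of the later value. Baseline and later variances are taken as equal for the change score.

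**Formulas, with the variance of the later value set to 1.**

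- Later value alone: variance 1
- Change score: variance 2(1 − rho)
- ANCOVA with own baseline: variance 1 − rho²
- Difference detectable with 90% power: (1.960 + 1.282) × sqrt(2/86) × sqrt(variance) = 0.494 × sqrt(variance)
- Patients per arm giving ANCOVA the precision of 86 unadjusted: 86 × (1 − rho²), rounded up

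| | rho 0.3 | rho 0.5 | rho 0.7 |
|---|---|---|---|
| ANCOVA variance | 0.91 | 0.75 | 0.51 |
| ANCOVA SE relative to later value alone | 0.95 | 0.87 | 0.71 |
| Equivalent n per arm | 79 | 65 | 44 |
| Detectable difference, ANCOVA (0.49 SD unadjusted) | 0.47 | 0.43 | 0.35 |
| Change-score variance | 1.4 | 1.0 | 0.6 |

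**Power for an assumed 0.3 SD difference, 86 per arm, normal approximation.** The later value alone gives 50%. ANCOVA gives 54%, 62% and 79% at rho 0.3, 0.5 and 0.7. A change score gives 38%, 50% and 72%. So the change score is worse than the later value at rho 0.3, equal at 0.5 and better only above that. ANCOVA is never worse than either, apart from one degree of freedom.

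**Missing labs.** If only half the patients had postoperative labs (43 per arm, an assumption), power for 0.3 SD without adjustment falls from 50% to 28%, and with ANCOVA at rho 0.7 from 79% to 50%. Loss of labs on this scale would cost about as much as adjustment at rho 0.7 gains.

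**Are the baselines valid covariates?** Section 2.3 has the allocation envelope opened in the operating room just before surgery, so the preoperative labs precede knowledge of the arm. For temperature, section 2.3 says "Following trocar placement, initial insufflation will be performed at 6 mmHg for patients in the study group". That is compatible with a reading taken before gas, but no text states that the reading comes first.

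**The case against.** The strongest reply is that no named analysis is affected. No aim, sample size or stated conclusion rests on these variables; they are reached only by a catch-all sentence in a short plan. That stands, and it sets the priority.

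Several stronger readings are tempting, and the documents do not support them:

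- **That the plan tests raw later values.** It does not say so. The defect is an unspecified quantity and no planned adjustment.
- **That the unadjusted comparison is biased.** In the full randomised arms it is not. A chance imbalance in preoperative hemoglobin is already covered by the type I error rate.
- **That a known amount of power is lost.** The 0.5 SD in section 2.4 is a pain-score effect size, so it says nothing about the power of a hemoglobin or creatinine comparison. Low rho cannot be excluded either, because the preoperative labs have no time window.
- **That all three baselines precede insufflation.** This is clear for the labs but only implied for temperature.
- **That adjustment solves the problem of labs taken in some patients only.** The documents give no criterion for taking them. If it depends on the postoperative course, or on staying overnight (length of stay is itself Aim 4), the subset with labs is selected after randomisation. Preoperative hemoglobin cannot undo that.

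What survives is that the baselines are collected, the plan does not use them, and a better analysis is available without new data.

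**Conclusion.** The point holds as a low-priority improvement in precision. The documents establish that the baseline values exist, that the general two-group rule is the only one reaching the later values, and that the regression in section 2.4 does not cover them. Adjustment would shrink the standard error by about 5% to 29% over an assumed rho of 0.3 to 0.7. The direction holds for any nonzero rho; the size cannot be fixed from the documents.

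A reader might infer that the plan's bleeding and renal results would be misleading. The documents do not support that: these are supporting variables, and in the full randomised arms the loss is precision only. The separate risk that postoperative labs exist for a selected subset is real, but it needs disclosure and cautious interpretation. Baseline adjustment does not remove it.

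**What to change.** In section 2.4, add that postoperative hemoglobin, postoperative creatinine (log scale if skewed) and end-of-procedure core temperature will each be compared between randomised arms by linear regression. The later value is the outcome and the patient's own baseline value is the covariate; report the adjusted difference with its 95% CI. A plain change score is not a safe substitute, because it loses precision when rho is below 0.5.

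State whether the baseline temperature is read before the assigned pressure is applied, since a reading taken afterwards could absorb part of the effect.

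Beside the hemoglobin and creatinine results, report the number of patients with postoperative labs in each arm, and note that adjustment does not remove selection if taking labs depends on the postoperative course.

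The cost is a few sentences of SAP text and one model per variable. It needs no added patients, visits or tests.

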	

ii. Wound infection (y/n)

c. Length of stay (days; typically 0 to 1)

i. Discharge date/time (m-d-y; hh:mm)

3. Use of postoperative pain medication

a. Opioids (y/n for each: fentanyl, Dilaudid, oxycodone, Norco, tramadol, Percocet, Demerol)

i. Morphine equivalents (MME)

b. Non-opioids (y/n for each: Toradol, Tylenol, oxybutynin)

4. Postoperative pain scores (0-10; asleep, missed, or discharged)

a. Average and maximum scores during each interval (during the PACU stay, the first 4 hours on the floor, next 8 hours, and the following 8 hours; as well as the final score immediately prior to discharge)

b. At each location (abdomen, legs, groin, scrotum, shoulder, other/specify)

5. Timing of ability to pass gas (day 0, day 1, day 2, >day 2)

6. Clinically-significant ileus (i.e., requiring treatment; y/n)

Follow-Up (1 week, 1 month, & 3 months)	

1. QoR-15 (0-150) – only asked at week 1

a. Collected (y/n)

b. Score (0-150)

2. Prescription(s) given (y/n) – only asked at week 1

a. Prescription(s) filled (y/n)

b. Opioids (y/n for each: fentanyl, Dilaudid, oxycodone, Norco, tramadol, Percocet)

i. Number of pills taken for each (#)

ii. Morphine equivalents (MME)

c. Non-opioids (y/n for each: Toradol, Tylenol, oxybutynin)

3. Scrotal swelling (y/n) – only asked at week 1

4. Leg weakness (y/n)

a. Left, right, bilateral

b. Degree of weakness (each leg; mild, moderate, severe)

c. Impaired ability to walk

d. Impaired ability to drive

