Patients that are unable to pass gas while inpatient will be called on postoperative day 1 (if discharged same-day only) and day 2. The post-operative day 1 phone call will also be utilized to assess pain for those who were discharged same-day, as explained above. If a patient confirms that they have passed gas on day 1, they will not be called again on day 2. For Thursday/Friday procedures where days 1 and/or 2 (as applicable) fall on the weekend, patients will be called on Monday morning and asked to recall when they were able to pass gas (i.e., whether it occurred on Saturday or Sunday). If patients are not discharged same-day, they will only receive a single phone call on day 2 if they did not pass gas prior to discharge. Patients who are not discharged same-day and are able to pass gas prior to discharge will not receive any phone calls. In the case that a patient is still unable to pass gas on day 2, we will repeat phone calls daily until they are able to do so, although we do not anticipate many patients will need to be called past day 2. We are collecting this data due to recent anecdotal evidence in Robotic Urology that patients who receive Percocet were able to pass gas on average in 1.6 days versus 1.4 days for those that did not receive Percocet.

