**Aim #4) Compare average length of stay (typically 0-1 days) between groups.**

The average length of stay postoperatively will be compared between the two groups using independent sample t-test or Mann-Whitney U test, as appropriate. Also, the proportion of patients in each group who went home on day 1 versus day 0 will be compared using Chi-square test or Fisher's exact test, as appropriate. A difference of 10% in the proportion of patients will be considered clinically significant.

A p-value of less than 0.05 will be considered statistically significant for analysis. All of the analyses will be performed using SAS Enterprise Guide, version 7.1 (SAS Institute, Cary, NC).

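### The plan names no ordered test for outcomes recorded as ordered categories (day of first passing gas, smoke evacuation quality); by default they fall under Chi-square or Fisher, which ignore order

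*Combined protocol and SAP*

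**What the plan says.** Section 2.4 has two general test rules. Continuous variables get a t-test or Mann-Whitney U. For the rest, "categorical variables will be compared using Chi-square test or" Fisher's exact test. No trend test, ordinal model or rule for ordered categories appears anywhere in the section. The threshold is common to all analyses: "A p-value of less than 0.05 will be considered statistically significant for analysis".

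Table 1 (section 2.2) lists three items with ordered levels:

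- Postoperative item 5, "Timing of ability to pass gas (day 0, day 1, day 2", with a fourth level for anything later than day 2.
- Intraoperative item 10, "Smoke evacuation quality (below average, average, above average".
- Follow-Up item 4b, "Degree of weakness (each leg; mild, moderate, severe", which sits beneath a yes/no question on leg weakness.

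None of the three belongs to Aims 1 to 4 or has its own analysis paragraph. Section 2.3 describes the telephone follow-up for gas timing. For patients who have still not passed gas on day 2, "we will repeat phone calls daily until they are able to do so". The same paragraph cites an anecdotal comparison of this outcome in mean days (1.6 versus 1.4), by Percocet use and not by pressure arm.

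**The concern.** Pearson's Chi-square and Fisher's exact test give the same result if the columns of the table are shuffled. A move of patients from day 2 to day 1 counts no more than an equally large scatter with no direction. The background in section 1.1 expects lower pressure to help patients, so a consistent shift towards earlier recovery is the natural alternative. Against that alternative, a four-level Chi-square spreads its sensitivity over 3 degrees of freedom where an ordered test uses one.

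At stake is some power on secondary descriptive outcomes. There is also an analyst's choice left open: because the class of gas timing is not stated, the test could be settled after the data are seen. The plan names no effect estimate for these outcomes either.

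**Working it through.** **The plan's own figure.** The only sizing is for the pain score at 5-12 hours: "The average score in the 6 mmHg group was 3.2, and that in 15 mmHg historical group was 3.9", with SD 1.4, "at a significance level of 0.05 to achieve 90% power". Two-sided, n = 2 × (1.960 + 1.282)² × (1.4/0.7)² = 2 × 10.51 × 4 = 84.1, so 85 per group. The t-based solution is 85.03, rounded up to 86, with power 0.906. Enrolment is 172/0.9 = 191.1, so 192, or 96 per arm. The stated figures reproduce. None of them concerns an ordered categorical outcome.

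**Inputs assumed, because the documents give none.** Control distribution of gas timing 10/45/30/15% on day 0/1/2/later. The study arm differs by a common odds ratio (OR) applied to every cumulative odds. Two-sided alpha 0.05, with 86 (planned evaluable) or 96 (enrolled) per arm.

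**Worked example, OR 2.**

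- Control cumulative proportions: 0.10, 0.55, 0.85. Odds: 0.111, 1.222, 5.667.
- Doubled: 0.222, 2.444, 11.333. Back to proportions: 0.182, 0.710, 0.919.
- Study arm: 18.2/52.8/20.9/8.1%.
- Scoring the levels 0 to 3, the means are 1.50 and 1.19, a shift of 0.31 days. OR 1.5 gives a shift of 0.18 days and OR 1.6 gives 0.21.

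**Simulated power, four levels** (40,000 tables per cell; Pearson Chi-square on 3 df against tie-corrected Mann-Whitney):

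| OR | Per arm | Chi-square | Mann-Whitney | Loss, points |
|---|---|---|---|---|
| 1.0 | 86 | 5% | 5% | 0 |
| 1.5 | 86 | 19% | 29% | 10 |
| 1.6 | 86 | 24% | 37% | 13 |
| 2.0 | 86 | 50% | 68% | 18 |
| 1.7 | 96 | 34% | 50% | 16 |
| 2.0 | 96 | 55% | 72% | 17 |
| 2.5 | 96 | 81% | 92% | 11 |

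**Asymptotic check.** For 80% power the noncentrality needed is 7.85 on 1 df and 10.90 on 3 df, a ratio of 10.90/7.85 = 1.39. Where an ordered test has 50, 60, 70 or 80% power, a 3-df test with the same noncentrality has 34.5, 43.2, 53.1 or 64.5%. The loss is 15.5 to 17 points, in line with the middle of the table.

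**Three levels** (assumed 20/60/20%, 86 per arm). OR 1.5: 20% against 26%. OR 2: 52.5% against 63%. The loss is about 6 and 10.5 points. Over the three-level distributions tried, it peaked at about 11.

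**How far it moves.** Over several assumed four-level distributions and odds ratios from 1.25 to 4, the loss ran from under 1 point to about 20. It is small when both tests have very low or very high power.

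**Where the ordered test is worse.** For 10/50/30/10% against 15/35/45/5%, which is not a consistent shift, Chi-square has 60% power and Mann-Whitney 7% at 86 per arm.

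**The case against.** The best counter-argument is that the plan does not assign gas timing to the categorical class. It already offers Mann-Whitney for discrete ordered measures such as 0-10 pain scores and length of stay in days, and section 2.3 speaks of gas timing in mean days. An analyst could use Mann-Whitney without departing from the plan. This stands as far as it goes: a reader might infer that the protocol prescribes an unordered test for gas timing, and no sentence says so. But the variable as recorded is a set of categories with an open-ended top level, and the only rule stated for categories is Chi-square or Fisher. That makes the unordered test the default reading.

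Three further inferences are tempting and not supported.

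- *A general loss of 15 to 18 points.* This holds only for four levels at mid-range power. The one documented difference in gas timing is 0.2 days, and it is not between pressure arms. A shift of about that size costs 10 to 13 points at 86 per arm, and either test would probably miss it.
- *A significant Chi-square would hide which arm recovered sooner.* Section 2.4 commits to frequencies and percentages for categorical variables. Tabulated by arm, these would show the direction of a consistent shift.
- *The top category wastes the daily calls.* Section 2.3 expects few patients to need calls past day 2, and weekend days are recalled on Monday. The data collection forms are not in the supplied text, so whether the exact day is kept cannot be seen.

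**Conclusion.** The point holds as a minor gap in specification. The plan states no ordered test, and for gas timing and smoke evacuation quality the default reading is a test that ignores order. If the arms differ by a consistent shift, this costs roughly 10 to 18 points of power for the four-level outcome at odds ratios of 1.5 to 2, and about 10 points or less for a three-level outcome. These sizes rest on assumed distributions and odds ratios, not on figures in the documents. The outcomes lie outside the four Aims and the sample size does not depend on them, so no main conclusion of the trial is threatened.

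**What to change.** Add to section 2.4:

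> Ordered categorical variables (day of first passing gas, smoke evacuation quality) will be compared by the tie-corrected Mann-Whitney U test, with a proportional-odds ratio and 95% CI. Chi-square or Fisher's exact test is kept for unordered variables.

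If leg weakness is added to that list, define it at each visit for all randomised patients as none, mild, moderate or severe, taking the worse leg. Without a level for no weakness, the test would compare only patients who developed weakness, a subset formed after randomisation.

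The cost is one sentence, plus a short definition if leg weakness is included. No extra patients, visits or calls are needed. The price is lower sensitivity to a difference that is not a consistent shift; the protocol hypothesises none. Recording the actual day beyond day 2 is optional and likely to matter little.
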